### **7.2.4 Genetic Analyses**

Genotyping will be carried out by [name] at Yale University. Blood will be coded and shipped to [name] lab at Yale University. Samples will be shipped without identifiers, on dry ice following University of Pennsylvania and international shipping procedures. Staff will send blood shipments in batches and verify that shipments arrived at the lab maintaining tracking logs of all samples sent. DNA will be purified from whole blood using the PureGene kit (GentraSystems, Minneapolis, MN). We typically obtain ~30mg of high-quality DNA per ml of blood extracted. TaqMan allelic discrimination assays have been designed (for the SNPs already examined) or will be designed (for SNPs still to be examined, e.g., in *GRK1*) using Primer Express 3.0 software (Applied Biosystems Inc.). Genotyping will be performed using the 5'-nuclease TaqMan closed-tube fluorescence method and an ABI 7500 Sequence Detector System for post-PCR plate reads.

## **7.3 Subject Population for Analysis**

Protocol-compliant subjects' data will be used for analysis.

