### **4.4 Early Withdrawal of Subjects**

#### **4.4.1 When and How to Withdraw Subjects**

Subjects with severe psychological symptoms (e.g., suicidal thoughts), those who fail to adhere to protocol requirements, and those withdraw consent will be withdrawn from the study and if applicable, referred for appropriate clinical care. If a subject is found to be pregnant during screening or during study, she will immediately be withdrawn from the study, referred for obstetric evaluation, and advised to discontinue all drinking.

Any subject experiencing a serious adverse event felt to be related to study drug should be withdrawn from the study.

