#### **4.4.2 Data Collection and Follow-up for Withdrawn Subjects**

We will make a strong effort (via phone calls and alternative contact information) to obtain follow-up information on all subjects who are prematurely withdrawn from the project.

CONFIDENTIAL

This material is the property of the University of Pennsylvania. Do not disclose or use except as authorized in writing by the study sponsor

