**Table 1. Medication Dosing Schedule for Topiramate**

	Medication Dispensed	Morning Dose	Evening Dose	Total Daily Dose
Screening Visit -0	Week 0	No medication	No medication	0 mg
Scan 1/ Visit 1	Week 1	No medication	25 mg	25 mg
Visit 2	Week 2	25 mg	25 mg	50 mg
Visit 3	Week 3	25 mg	50 mg	75 mg
Visit 4	Week 4	50 mg	50 mg	100 mg
Visit 5	Week 5	50 mg	100 mg	150 mg
Visit 6	Week 6	100 mg	100 mg	200 mg
Scan 2/Visit 7	Week 7	100 mg	100 mg	200 mg
Taper Visit 8	Week 8	Reduce dose by 50 mg every 2 days (150 mg for 2 days, 100 mg for 2 days, 50 mg for 2 days, then D/C		
Final visit/Visit 9	Week 9	No medication	No medication	0 mg

If subjects experience significant side effects from the study drug (topiramate or placebo), the investigators will have the option to reduce the dose (number of pills) during the study, based on consultation with the research staff, or as clinically indicated, by interviewing the subject directly. All dosing is on a double blind basis, thus, the physician can vary the number of capsules of placebo or topiramate in response to adverse effects reported by the subject. Upward titration following a dose reduction will be allowed once during the trial. Dose titration, if necessary, will be carefully documented in the study chart along with the clinical rationale.

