## **6.5 Laboratory/MRI Session 2 Visit (approximately 3.5 hours)**

During week 7, subjects will complete the 2nd scanning session. Procedures for the Laboratory/MRI Session 2 visit are the same as the 1st Laboratory/MRI Session procedures.

Early Termination Visit:

All patients (including those who discontinue treatment prematurely) will be asked to complete an end-of-treatment evaluation and to complete all scheduled assessments to facilitate intention-to-treat (ITT) analyses. All patients will be informed of these procedures prior to study enrollment. Patients will be compensated \$50 for completing the end-of-treatment visit. Patients who decide to terminate the study prior to week 8 will also receive \$50 upon completion of the end-of-treatment procedures. For patients who withdraw early and do not wish to continue with study visits/procedures, all end-of-treatment procedures will be administered at the time of withdrawal. Such patients will also be asked to undergo in-person or telephone follow-up at end-of-treatment for collection of the remaining treatment-phase Timeline Follow-back data.

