#### 7.2.2 Imaging Data Analyses

Global CBF time course will be included in the model as a covariate to examine the effects of topiramate on regional CBF. No temporal smoothing will be applied. Contrasts between conditions (alcohol cue vs non-alcohol cue; scan 1 vs scan 2) will be defined in the general linear model to assess the voxel by voxel CBF difference. Using the corresponding parametric maps of this contrast ( $\beta$  maps), random effects analysis will be employed to test for a significant main effect of condition with a statistical parametric map of the T statistic at each voxel for population inference for each session for the placebo and topiramate groups (second-level analysis). A 2x2 factorial design matrix will be used to assess the effects of the pharmacological manipulation by including the group (topiramate vs placebo) and condition (scan 1 vs scan 2) as the two factors. An associated contrast will be defined in this model to examine administration effects. This two-stage analysis is theoretically equivalent to a 2-way analysis of variance (ANOVA). Simple regression analyses will be conducted on CBF with the change in craving scores [post-alcohol cue minus pre-alcohol cue craving scores, number of heavy drinking days during the past 30 days, and age] as covariates of interest to test for prognostic brain/behavioral correlations. For the exploratory aim, subjects will be grouped by genotype (CC vs A-allele carrier) to examine the moderating effects of rs2832407 in

CONFIDENTIAL

This material is the property of the University of Pennsylvania. Do not disclose or use except as authorized in writing by the study sponsor

*GRK1* on topiramate effects using the same simple regression analyses described above. We will limit this analysis to European Americans, as that is the population in which the preliminary findings were obtained and allele frequencies differ significantly by population.

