### **8.6 Protection of Subjects**

Complementing the safety measures noted above, additional procedures will be followed to protect the safety of the research subjects. Potential Subjects will be screened for medical illnesses that would preclude the use of topiramate. Subjects selected for the study will be evaluated weekly while receiving study drug treatments. AEs will be monitored weekly and a study physician will be available at all times to evaluate and treat adverse effects of the medication. On a weekly basis weights and vital signs will be obtained.

CONFIDENTIAL

This material is the property of the University of Pennsylvania. Do not disclose or use except as authorized in writing by the study sponsor

Significant AEs will result in exclusion from the study. Venipuncture will be carried out with good aseptic technique by an experienced phlebotomist, nurse, or physician. Venipuncture sites will be monitored carefully for signs of infection. At the conclusion of randomized medications, a physical examination, STUDY LABORATORY TESTS, and a urine pregnancy test (if female of childbearing capability) will be performed. Subjects will be given a 24-hour emergency number they can call if necessary. The PI or study psychiatrist will clinically follow all subjects who are discontinued due to a serious AEs until the AE resolves and becomes completely stable, unless a referral to another physician (i.e. specialist) is clinically indicated or requested by the subject.

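### Section 7.3 limits all analysis to an undefined protocol-compliant subset, while Section 6.5 collects discontinuers' data for intention-to-treat analyses that Section 7 never plans

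*Combined protocol and SAP*

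**What the plan says.** - **Analysis set.** Section 7.3 reads in full: "Protocol-compliant subjects' data will be used for analysis". It is the only analysis population the protocol names.
- **Data collection.** Section 6.5 (Early Termination Visit) asks all patients, whether or not they stay on treatment, "to complete all scheduled assessments to facilitate intention-to-treat (ITT) analyses". Early withdrawers are also asked for "follow-up at end-of-treatment for collection of the remaining treatment-phase Timeline Follow-back data". Section 4.4.2 promises a strong effort "to obtain follow-up information on all subjects who are prematurely withdrawn from the project".
- **Removal from the study.** Under Section 4.4.1, "those who fail to adhere to protocol requirements, and those withdraw consent will be withdrawn from the study". Section 8.6 adds: "Significant AEs will result in exclusion from the study".
- **Dose and adherence.** Under Section 5.2, if side effects are significant, "the investigators will have the option to reduce the dose (number of pills) during the study". Section 5.5 provides for weekly pill counts but gives no cut-off.
- **Arm comparison.** Section 7.2.2: "A 2x2 factorial design matrix will be used to assess the effects of the pharmacological manipulation", with group and scan as the two factors. Heavy drinking days appear in that section only as a covariate in regressions on CBF.
- **Blinding.** Section 5.8 keeps subjects and research staff blinded until after database lock.

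**The concern.** The study is randomised, double-blind and placebo-controlled, and Hypothesis 2a is tested by comparing arms. Restricting that comparison to subjects judged compliant after randomisation removes its protection if compliance is related to change in CBF and the exclusions differ by arm in number or in kind. Sections 4.4.1 and 8.6 make arm-related exclusion plausible, because adverse events can depend on treatment. Section 1.4 gives, from other trials, numbness and tingling in 49% versus 6% and cognitive effects in 28% versus 10%. Those are not exclusion rates for this study.

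There is also a conflict within the document. Subjects are asked for data for a stated intention-to-treat purpose, and the statistical section never uses the data that way. This affects drinking as well as imaging: Hypothesis 2b concerns reductions in heavy drinking days, and drinking can be recorded by telephone after withdrawal even when a scan cannot.

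**Working it through.** **Step 1: what the text settles.** Section 6.5 contains the only mention of intention-to-treat. Sections 7.1 to 7.3 name no all-randomised set, no missing-data method and no sensitivity analysis. The image check in 7.2.1 (movement, complete acquisition) is quality control, not a compliance rule. No effect size, SD, power or dropout rate is stated, so there is no planned figure to reproduce.

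**Step 2: what the missing definition changes.** Take three readings of protocol-compliant and two randomised subjects, each with two usable scans.

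| Reading | Subject with a permitted dose reduction | Subject who stopped drug but completed the assessments 6.5 requests |
|---|---|---|
| Not withdrawn under 4.4.1 | In | Unclear: non-adherence is itself a ground for withdrawal |
| Pill-count cut-off | Depends on how the reduction is counted | Likely out |
| Reached and held 200 mg/day | Out | Out |

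The same data can enter or leave the CBF test depending on a choice the protocol does not make.

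**Step 3: what rewording 7.3 can and cannot recover.** A subject removed under 4.4.1 or 8.6 before week 7 may have no Scan 2 and is then missing from the scan contrast under any analysis set. Section 6.5 says that early withdrawers who do not wish to continue have end-of-treatment procedures at the time of withdrawal. It does not say whether these include the MRI, or whether such a scan would count as Scan 2. For drinking, the data exist wherever the requested follow-up succeeds.

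**Step 4: illustration of bias under assumed rates.** Inputs from the protocol: 20 randomised per arm and alpha .05 (taken as two-sided). Assumed: no drug effect; a two-sample t-test on Scan 2 minus Scan 1; one comparison with no voxel-wise threshold; exclusion of the subjects at one end of a trait correlated r with change; all exclusion rates.

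Dropping the k most extreme of 20 leaves a mean trait of size m(k), the sum of the k largest expected normal order statistics divided by (20 − k):
- k = 2 (10%): (1.867 + 1.408)/18 = 0.182
- k = 4 (20%): 5.327/16 = 0.333
- k = 6 (30%): 6.662/14 = 0.476
- k = 8 (40%): 7.425/12 = 0.619

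The size of the bias in SD of change is r × [m(topiramate) − m(placebo)] if both arms lose the same end of the trait, and r × [m(topiramate) + m(placebo)] if they lose opposite ends. Rejection rates are from 20,000 simulated trials per scenario.

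| Excluded, topiramate vs placebo | r | Ends lost | Bias (SD) | Rejection |
|---|---|---|---|---|
| None | – | – | 0 | 4.8% |
| 20% vs 10% | 0.2 | same | 0.2 × (0.333 − 0.182) = 0.03 | 4.9% |
| 30% vs 10% | 0.3 | same | 0.3 × (0.476 − 0.182) = 0.09 | 5.9% |
| 40% vs 10% | 0.5 | same | 0.5 × (0.619 − 0.182) = 0.22 | 9.7% |
| 30% vs 10% | 0.3 | opposite | 0.3 × (0.476 + 0.182) = 0.20 | 8.7% |
| 40% vs 10% | 0.5 | opposite | 0.5 × (0.619 + 0.182) = 0.40 | 20.0% |
| 20% vs 20% | 0.3 | same | 0.3 × (0.333 − 0.333) = 0.00 | 5.3% |
| 20% vs 20% | 0.3 | opposite | 0.3 × (0.333 + 0.333) = 0.20 | 9.3% |

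A trait that raises or lowers both scans equally cancels in the difference: bias 0.00 SD, rejection 5.0 to 5.2%. Equal exclusion counts do not guarantee safety, as the last row shows, so reasons matter as well as counts.

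These figures treat every excluded subject as lost because of 7.3. Some would have no Scan 2 in any case, so the table does not measure the effect of 7.3 alone.

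**The case against.** The strongest reply is that this is a mechanistic pilot that describes itself as not a treatment trial. It asks what topiramate does to CBF, and subjects who took the drug are a reasonable group in which to ask. That justifies keeping a compliant-set analysis, provided the set is defined in advance. It does not justify leaving the set undefined, or making it the only analysis when 6.5 gathers data for a different one.

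Three stronger readings are tempting, and the documents do not support them:

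- **That the CBF result will be biased, by as much as 0.40 SD or a 20.0% false-positive rate.** That case needs 40% versus 10% exclusion, r = 0.5 and opposite ends lost. The protocol gives no exclusion rates, and Section 1.5 reports 200 mg/day as well tolerated in an earlier trial.
- **That rewriting 7.3 restores a full intention-to-treat imaging analysis.** Subjects without a Scan 2 stay missing. The sentence in 8.6 concerns participation, and its effect on scan availability survives any change to the analysis set.
- **That the set can freely be chosen to suit the results.** Blinding until after database lock narrows that risk. It does not remove it, because no definition has to be written before the codes are opened.

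**Conclusion.** The point holds as a defect of definition and consistency. The sole analysis set is undefined, depends on events after randomisation, and conflicts with the stated purpose of the data collection in 6.5. Usable data from randomised subjects could be left out of the CBF comparison and the drinking analysis.

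Bias in the arm comparison is possible, not shown. It requires exclusion that is related to the outcome and differs by arm in rate or kind. Its size cannot be derived from the documents: under the assumed scenarios it runs from none to 0.40 SD, and part of that would come from missing scans rather than from 7.3. The textual finding rests on no assumption beyond the plain reading that compliance with drug, visits and Scan 2 is known only after randomisation. It should be fixed before the blind is broken.

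**What to change.** 1. Rewrite 7.3 so that the main analyses use all randomised subjects with available data, in their assigned arm, regardless of adherence, dose reduction or treatment discontinuation. For CBF, this means all with usable scans. For heavy drinking days, it means all with Timeline Follow-back data, including data collected after withdrawal. Where drinking is related to CBF change, it means all with both.
2. State whether a scan done at early withdrawal counts as Scan 2.
3. In 7.2.2, require missing or unusable scans to be reported by arm with reasons.
4. Keep a protocol-compliant set as a sensitivity analysis, with its definition written before the blind is broken, including how a permitted dose reduction is classed.
5. Reconcile 4.4.1, 6.5, 7.3 and 8.6 so that it is clear whose data continue to be collected and whose are analysed. This concerns data only and takes no position on when treatment should stop.

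Cost: text edits and a little extra analysis work. Section 6.5 already requests the scheduled assessments and follow-up drinking data; whether it also requests a scan at early withdrawal is what item 2 must settle. The downside is some dilution of the pharmacological effect in the main analysis, which the compliant-set analysis addresses.

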# **8 Safety and Adverse Events**

## **8.1 Definitions**

### **Adverse Event**

An **adverse event** (AE) is any symptom, sign, illness or experience that develops or worsens in severity during the course of the study. Intercurrent illnesses or injuries should be regarded as adverse events. Abnormal results of diagnostic procedures are considered to be adverse events if the abnormality:

- results in study withdrawal
- is associated with a serious adverse event
- is associated with clinical signs or symptoms
- leads to additional treatment or to further diagnostic tests
- is considered by the investigator to be of clinical significance

### **Serious Adverse Event**

Adverse events are classified as serious or non-serious. A **serious adverse event** is any AE that is:

- fatal
- life-threatening
- requires or prolongs hospital stay
- results in persistent or significant disability or incapacity
- a congenital anomaly or birth defect
- an important medical event

Important medical events are those that may not be immediately life threatening, but are clearly of major clinical significance. They may jeopardize the subject, and may require intervention to prevent one of the

CONFIDENTIAL

This material is the property of the University of Pennsylvania. Do not disclose or use except as authorized in writing by the study sponsor

other serious outcomes noted above. For example, drug overdose or abuse, a seizure that did not result in inpatient hospitalization, or intensive treatment of bronchospasm in an emergency department would typically be considered serious.

All adverse events that do not meet any of the criteria for serious should be regarded as ***non-serious adverse events***.

#### **Adverse Event Reporting Period**

The study period during which adverse events must be reported is normally defined as the period from the initiation of any study procedures to the end of the laboratory/scan session (approximately 2 weeks from informed consent).

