## 3 Study Design

### 3.1 General Design

- **Phase IV Study** - This is a phase IV research study aimed at identifying the brain and behavioral mechanisms underlying the GABA/glutamate modulator, topiramate.
- **Design** – Heavy drinkers who meet DSM-5 criteria for AUD and express an interest in reducing or stopping drinking will be recruited, screened, consented, and if eligible, will complete a randomized double-blind, placebo-controlled study of topiramate ( $N=40$ ; topiramate 200 mg/day:  $n=20$  or placebo:  $n=20$ ). Topiramate or placebo will be initiated after Scan 1 and continued with weekly visits and medical management [33]. During the 7th week, participants will complete Scan 2 followed by medication taper and an endpoint visit. We will use perfusion fMRI during alcohol cue exposure to acquire brain and behavioral responses to alcohol cues. The goals of this study are to pilot test the validity of our alcohol cues and to identify brain and behavioral mechanisms of topiramate in reducing heavy drinking in alcohol dependent individuals.
- **Study Duration** – The duration of this study will be approximately 9 weeks, including screening, Scan 1, 8 weeks of medication and medical management (including medication taper), Scan 2 during week 7, medication taper, and an endpoint visit. The entire study will run for approximately 24 months.

CONFIDENTIAL

This material is the property of the University of Pennsylvania. Do not disclose or use except as authorized in writing by the study sponsor

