#### **6.4 Weekly Visits (approximately 50 minutes)**

At each weekly visit, subjects in both medication groups will receive medical management (MM) [33]. This provides a basic clinical intervention that was designed to be used in conjunction with prescribed medication, and to be easily implemented by medically trained practitioners in non-specialty settings. The treatment will support subjects' efforts to reduce their drinking.

The first session (conducted right after the first MRI scan) will consist of a review of the results of the initial evaluation, identifying any medical concerns. This session will also use the brochure *A Guide to Sensible Drinking*, developed for use in the World Health Organization Brief Intervention Study project. The subject is then provided with a rationale and information about pharmacotherapy and the importance of adherence. At each visit, assessment and counseling (lasting approximately 15 minutes) are conducted. During these sessions, the nurse will perform a medical check on the subject's general functioning, obtain vital signs and weight, ask about medication side effects and concurrent medications, monitor the subject's medication adherence, and as appropriate, make recommendations on strategies for medication adherence for the subject to follow until the next visit. Men will be advised to consume no more than 4 standard drinks per day and 12 standard drinks per week and women will be advised to consume no more than 3 drinks per day and 8 drinks per week. Because subjects will not be physically dependent on alcohol, reduction of heavy drinking is a safe and ethical goal. The research technician or coordinator will measure the subject's breath alcohol concentration, perform a brief assessment of the subject's drinking, review the self-administered BDI to assess suicidal thoughts/ideation (and discuss with the nurse and/or physician, if there is endorsement of suicidal thoughts). For patient safety during travel, subjects will be instructed not to drink prior to study visits. At each visit, the subject's BrAC, weight, and vital signs will be measured. Subjects must have a breath alcohol level of 0.00 g% to complete the screening visit, 2 lab MRI scan visits, and endpoint visit, and below 0.05 g% to complete the weekly study visits. Study staff will follow TRC standard operating procedures for all subjects that present with a breath alcohol level above 0.00 g% at study visits.

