Throughout the study, if a subject misses a study visit due to a vacation or an unforeseen event, the study nurse will provide the subject with enough study medication to ensure that he or she will be able to maintain the daily dosage of study medication until the next scheduled visit. The nurse will also provide instructions on how to take the study medication as per the dosing schedule. Study nurses will instruct subjects to call the TRC at any time to discuss any problems or concerns they may have while taking the study medication. All subjects will be provided phone numbers to contact the study staff during office hours and the beeper number for off-hours contact 24 hours a day. Subjects will be asked to come in for their next study visit as soon as possible.

If a subject calls to cancel a scheduled study visit due to an unforeseen event, study personnel will reschedule the study visit for as soon thereafter as possible. Study staff will mail the study medication to the subject via registered mail under the supervision of a study nurse. Staff will mail the study medication with the intent to reach the subject, before he or she runs out of study medication. The subjects will only be provided with enough study medication to ensure that they will be able to maintain their daily dosage of study medication until their next scheduled visit. The nurse will provide instructions over the phone on how to take the study medication as per the dosing schedule and record any adverse events that have occurred since the last study visit. Study nurses will instruct subjects to call the TRC at any time to

CONFIDENTIAL

This material is the property of the University of Pennsylvania. Do not disclose or use except as authorized in writing by the study sponsor

discuss any problems or concerns they may have while taking the study medication. Study staff will make efforts to reschedule missed study visits as soon as possible. An investigator will determine how many additional weeks of study medication a subject will be allowed to receive without attending a study visit.

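### Section 8.1 ends adverse event reporting about 2 weeks after consent, but study drug starts after Scan 1 and runs for 8 weeks

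*Combined protocol and SAP*

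**What the plan says.** Section 8.1 (Adverse Event Reporting Period) sets the window in one sentence. Mandatory reporting normally begins with the first study procedure and lasts "to the end of the laboratory/scan session (approximately 2 weeks from informed consent". No other section states a different period, and the sentence is not limited to the pilot.

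The main trial's calendar is in Section 3.1 and in Table 1 of Section 5.2. "Topiramate or placebo will be initiated after Scan 1 and continued with weekly visits and medical management", and each subject's course includes "8 weeks of medication and medical management (including medication taper), Scan 2 during week 7". Table 1 titrates from 25 mg/day in Week 1 to 200 mg/day in Weeks 6 and 7. Week 8 is a six-day taper ("Reduce dose by 50 mg every 2 days"), and the Endpoint Visit (Visit 9, Section 6.6) follows.

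Other sections keep AE work going throughout treatment. At weekly visits the nurse is to "ask about medication side effects and concurrent medications", and when a visit is cancelled is to "record any adverse events that have occurred since the last study visit" by telephone (Section 6.4). The first paragraph of Section 8.2 has staff ask about AEs at every contact and enter all of them in source and CRF, with no end date. Section 8.6 has AEs monitored weekly. The second paragraph of Section 8.2, however, ties its must-record rule to the *study period*, the term that Section 8.1 defines. For later events it names only serious adverse events (SAEs) judged possibly related.

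**The concern.** Taken literally, mandatory reporting ends before dosing starts or soon afterwards. The definition also affects other rules. The second paragraph of Section 8.2 and the pre-existing-condition rule in Section 8.1 both use *study period*. Section 8.5 refers back to the reporting rules above it, and the monitor checks reporting against the protocol's time periods (Section 10.1, item j).

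The events most exposed are non-serious AEs, and SAEs judged unrelated, that occur on study drug. The protocol expects mostly non-serious drug effects: Section 1.4 gives numbness and tingling in 49% against 6% on placebo, and cognitive effects in 28% against 10% in the migraine studies. AEs also lead to decisions, since Section 5.2 says "the investigators will have the option to reduce the dose (number of pills) during the study" and Section 8.6 provides for exclusion after significant AEs. If staff and monitor apply different windows, the AE record may be uneven over the weeks when it matters most.

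**Working it through.** **Inputs**
- Reporting window: about 14 days from consent (Section 8.1).
- First dose: evening of Scan 1/Visit 1 (Section 3.1, Table 1).
- Dosing: daily in Weeks 1 to 7, then 6 taper days (Table 1).
- Lag from consent to Scan 1: not stated, so 0 to 14 days is assumed. Section 6.2 allows up to 5 business days for the eligibility notice and Table 1 puts screening in Week 0, so lag 0 is only a bound.
- Also assumed: 7-day visit intervals and no dose reductions.

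**The plan's own durations.** Visit 9 falls at lag + 56 days. At lag 7 this is 63 days, or 9 weeks, which reproduces the approximate 9 weeks in Section 3.1; at lag 14 it is 70 days, or 10 weeks. The 2 weeks in Section 8.1 can match only Scan 1.

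**Dosing days** = 7 × 7 + 6 = 55. **Days at 200 mg** = Weeks 6 and 7 = dosing days 36 to 49 = 14.

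**Session read as Scan 1.** The first dose follows the scan, so 0 of 55 dosing days are covered.

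**Window read as 14 days from consent.** Dosing days inside = max(0, 14 − lag).

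| Lag (days) | Inside | Outside | Share outside | 200 mg days inside |
|---|---|---|---|---|
| 0 | 14 | 41 | 41/55 = 74.5% | 0 |
| 7 | 7 | 48 | 48/55 = 87.3% | 0 |
| 14 | 0 | 55 | 55/55 = 100% | 0 |

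The first 200 mg day is dosing day 36. Even at lag 0 the window would have to exceed 35 days to reach it, and 35/14 = 2.5 times the stated length.

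**Session read as Scan 2.** At lag 7, the first day of Week 7 is 7 + 42 = 49 days (7 weeks) from consent, not 2 weeks. Counting the scan-day dose as outside:
- Scan on dosing day 43 (strict 7-day intervals): days 43 to 55 = 13 outside, 7 of them at 200 mg.
- Scan on dosing day 49 (last day of Week 7): days 49 to 55 = 7 outside, 1 of them at 200 mg.

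Counting the scan-day dose as inside gives 12 and 6, and 6 and 0. All 6 taper days and the Endpoint Visit are outside in every case.

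No reading gives a 2-week period that covers the study drug.

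**The case against.** The strongest reply is that the protocol handles AEs adequately elsewhere. The window is only *normally* so defined, and an AE is defined in Section 8.1 over the whole course of the study. Besides the duties in Sections 6.4, 8.2 and 8.6, the principal investigator reviews AEs at least weekly (Section 10.1). Section 8.1 also covers end-of-study findings and later related events, and Section 8.6 requires an examination and tests when randomized medication ends. The 72-hour SAE rule in Section 8.3.1 has no end date and no relatedness condition. Section 9.1 uses *study period* for a subject's whole scheduled participation. The singular scan session resembles the one-scan pilot, which also relies on Section 8 (Appendix 1), so the sentence may be leftover wording.

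Much of this stands. It shows what the sponsor probably intends and makes a complete loss of AE data unlikely. The link from Section 8.5 and from item j of Section 10.1 to this window is an inference; item j could equally mean deadlines such as the 72 hours. The pilot origin is also an inference, and the pilot is described as about one week, not two.

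It does not remove the conflict. None of these provisions sets another reporting period, and no main-trial exception is stated. Section 8.3.1 protects SAEs in part, but the second paragraph of Section 8.2 names only possibly related SAEs after the *study period*, so unrelated ones remain open to two readings. The pilot is marked completed, so the sentence now serves only the main trial.

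**Conclusion.** The concern holds. The only AE reporting period in the protocol is incompatible with the treatment schedule and with the duties in Sections 6.4, 8.2 and 8.6. Most or all planned dosing days fall outside it: 48 to 55 of 55 for lags of 7 to 14 days, and 41 even at the lag-0 bound. No day at 200 mg falls inside on the 2-week reading. These counts rest on the assumed lag, 7-day visit intervals, no dose reductions and a hard cut at 14 days for an approximate figure. They count dosing days, not missed events.

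The consequence is a possible inconsistency in recording and checking non-serious AEs and unrelated SAEs on drug. Section 7 plans no between-arm AE comparison, so no planned analysis is biased. The point should be fixed, because following the sentence as written ends mandatory reporting before dosing or early in it.

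**What to change.** Reconcile Section 8.1 with Table 1 and Sections 6.4, 8.2 and 8.6. Restate the main-trial reporting period so that it covers all study drug, the taper and the Endpoint Visit (Visit 9), in line with the existing duty to ask at every contact. State that *study period* in Sections 8.1 and 8.2 means this period and that Section 8.3 applies throughout it. The post-study rules in Section 8.1 can stay as they are, and the completed pilot needs no separate window.

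The cost is one sentence in Section 8.1 and a one-line cross-reference in each of Sections 8.2 and 8.3. AEs are already sought at each contact, so no visit or test is added.
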